7.10 Co-enrolment Guidelines

To avoid potential confounding issues, ideally patients should not be recruited into other trials. Individuals that have participated in a trial testing a medicinal product within the three months preceding screening will be ineligible for the study. Where recruitment into another trial is considered to be appropriate and without having any detrimental effect on the MENDS trial this must first be discussed with the coordinating centre (MCRN CTU) who will contact the lead investigators ([name]/[name]).

8 ASSESSMENTS AND PROCEDURES

8.1 Summary

All patients will be recruited from outpatient clinics of specialist centres. Potential participants will generally be identified by community paediatricians, who will refer to specialist centres for review of sleep disorders. The community paediatricians will be engaged to provide potential participants with written information about the trial, including contact details if they require further information, and arrange for an out patient clinic appointment in the usual way.

Following fully informed written consent and assent (if appropriate) (Section 11.3) all eligible patients will be registered for the study and the family will be provided with a standardised booklet on basic sleep hygiene and behavioural techniques shown to help reduce sleeping difficulties, but no other intervention (behavioural, pharmacological or homeopathic), to try and improve their child's sleep. They will also be shown how to complete a 24-hour sleep diary and will be asked to complete this continuously over the next four weeks. In addition to this an actigraph will be provided, which the child will wear for the next four weeks to provide baseline data relating to wake and sleep periods.

Two weeks after registration a home visit will be undertaken by the RP, who will review progress with the sleep hygiene intervention. No formal assessment of progress will be undertaken and no further intervention will be commenced. A sub-study is also being undertaken that involves genotyping of all children initially recruited to the project with sleep disorders and developmental delay. As preliminary data suggests that autism may be particularly strongly associated with some of the genetic variants under investigation, we need to define this subgroup with more precision, this will be done using the Social Communication Questionnaire (SCQ) although it is acknowledged that this is a screening and not a diagnostic tool. Collection of DNA (see Appendix K) and completion of the SCQ will be subject to a separate consent and assent (if appropriate) process that will be undertaken at this home visit. Equipment will be provided for salivary sampling, which will be undertaken on the evening prior to the randomisation visit.

The child will be seen again in clinic a minimum of 4 weeks after registration and, if still fulfilling eligibility criteria, will be randomised into the study. The sleep hygiene period can be extended to a maximum of 6 weeks if required to allow flexibility in the scheduling of the randomisation clinic visit. Randomisation will require additional fully informed written consent and assent (if appropriate) (Section 11.3).

The trial duration for each participant is 12 weeks from date of randomisation and it is intended that all randomised patients will receive trial medication throughout their participation. At randomisation each patient will be allocated their own 'individual patient package' containing either melatonin or placebo. These packages will be retained in the pharmacy department of the relevant institution and issued on a weekly basis dependent upon dose to be administered. The child will be given the first dose and kept on that dose for a minimum of seven days. For the next three weeks and at each one-week interval during this time, the child's sleep disorder will be reviewed by the RP during home visits and the medication either left unchanged, increased to the next dose increment based upon the protocol dose modification criteria (see section 7.9.1) or decreased due to the presence of adverse events (see section 7.9.2). The decision to increase medication will be based upon the protocol dose modification criteria: (i) absence of Serious Adverse Events; (ii) a minimum of 5 of 7 days completed in the sleep diary; (iii) no significant increase in seizure activity (where applicable); (iv) child having received at least 5 of the possible 7 doses in the current week; (v) a) child not falling asleep within one hour of 'lights off' or 'snuggling down to sleep' at age-appropriate times for the child in three nights out of five, and/or b) child having less than 6 hours of continuous sleep in three nights out of five.

There are a maximum of 3 dose increments after the starting dose of 0.5 mg, through 2.0mg, 6.0mg and up to a maximum of 12.0mg. After seven days, the child will either be maintained on that dose if the sleep disorder has improved (i.e. the fifth dose modification criteria is no

longer met) or increased to the next dose if all dose modification criteria are met (see section 7.9.1). This process will be repeated after a further seven days until the third home visit after commencing study drug. If doses are increased at each home visit, the maximum dose threshold will be achieved by T+3W and for the remainder of the study, the child will remain on the dose achieved by the fourth week of treatment unless a reduction is indicated when reviewed at subsequent follow-up (see section 7.9.2). For children who have not achieved the maximum dose level in week T+3W, a dose increment at T+4W may also be considered. Dose increases in weeks T+5/T+6W are permitted with appropriate clinical review (see section 7.4.1) but are not permitted beyond this time.

8.2 Schedule for Follow-up

(See also Table 2)

TIME (weeks)

Study Schedule

T-4W:

Clinic visit (Clinician and RP). In the outpatient department, potential participants will be screened by the clinician and RP and those identified as being eligible for entry into the study on the basis of meeting the inclusion and exclusion criteria will be invited to allow the trial RP to complete assessments and provide the sleep hygiene/behavioural information. Following fully informed written consent (by RP or investigator) they will be registered in the study and allocated a unique registration number. At this stage participants are consenting only to be registered and undergo the 4 week sleep hygiene intervention and assessments.

Adhering to a scripted dialogue (Appendix H), the RP will provide the family with a standardised booklet on basic sleep hygiene and behavioural intervention. No other intervention (behavioural, pharmacological or homeopathic) to try and improve their child's sleep will be initiated. They will be shown how to complete a 24-hour sleep diary and will be asked to maintain a continuous sleep diary record over the next 4 weeks. Additionally, for patients with a diagnosis of epilepsy a seizure diary will also be maintained. The RP will supply the actigraph to be applied for the next four weeks, explaining how it is worn and operated.

The following questionnaires and assessments will be carried out:

- Adaptive Behaviour Assessment System (ABAS)
- Children's Sleep Habits Questionnaire (CSHQ)
- Composite Sleep Disturbance Index (CSDI)

Arrangements will be made for the RP to visit them at home at T -2W (i.e. after 2 weeks of basic sleep hygiene and behavioural intervention)

T-2W:

Home visit 1 (study nurse). The RP will visit the home to discuss progress, although no additional sleep intervention advice will be provided. The actigraph will be downloaded, visually compared with the sleep diary and re-initialised. Reasons for major discrepancies with the sleep diary will be recorded.

For those who consent (separate consent process carried out at this visit), the following will be carried out:

- Collection of DNA sample (saliva sample)
- Completion of Social Communication Questionnaire

Equipment will be provided along with verbal and written explanations for undertaking the salivary melatonin collection, which will be carried out on the evening prior to the T0W clinic visit and at T+10W (see

section 8.6.3 and Appendices D and E [instructions for collection]). The analysis of both sets of samples will be carried out at the same time at the end of the study.

T0W: **Clinic visit (Clinician review).** Children will be reviewed in the outpatient clinic and their sleep pattern (as reported by their family) and sleep diaries will be reviewed to decide whether they are still eligible for the study. Actigraph data will be downloaded and visually compared with the sleep diary but will not be analysed at this time and the actigraph will be removed. Reasons for major discrepancies with the sleep diary will be recorded. Prior to T0 consent and randomisation a single sheet form will be completed to evaluate which aspects of the advice given in the sleep hygiene booklet parents have put into practice. The responses to this evaluation will not influence whether or not the child is randomised.

Assuming the child continues to fulfil the entry criteria and fully informed written consent is provided; the child will then be randomised into the study.

The following baseline questionnaires and assessments will be carried out after consent and prior to randomisation:

- Composite Sleep Disturbance Index (CSDI)
- Children's Sleep Habits Questionnaire (CSHQ)
- Family Impact Module of PedsQL™
- Epworth Sleepiness Scale
- Aberrant Behaviour Checklist (ABC)

Upon randomisation the child will be allocated a unique randomisation number and their trial treatment. The randomisation number supersedes the registration number and will be used on all subsequent trial records.

Two week's supply of study medication will be dispensed (to allow for any delay in visit 2); to be administered 45 minutes before the child's age-appropriate 'lights off' or 'snuggle-down-to-sleep' time.

T+1W: **Home visit 2 (RP).** Child and sleep diary reviewed; medication increased or maintained*, based upon sleep diaries; TESS review; seizure diary review.

* Decision based upon the protocol dose modification criteria (Section 7.9)

T+2W: **Home visit 3 (RP).** Child and sleep diary reviewed; medication increased, maintained or decreased according to dose modification criteria (Section 7.9), based upon sleep diary; TESS review; seizure diary review.

T+3W: **Home visit 4 (RP).** Child and sleep diary reviewed; medication increased, maintained or decreased according to dose modification criteria (Section 7.9), based upon sleep diary; TESS review; seizure diary review.

T+4W: **Home visit 5 (RP).** Child and sleep diary reviewed; medication dose increased, maintained or decreased according to dose modification criteria (Section 7.9), based upon sleep diary; TESS review; seizure diary review.

- T+5W to T+6W** **Weekly telephone call (RP).** Child and sleep diary reviewed. Seizure diary (if applicable) and TESS review. Medication dose increased, maintained or decreased according to dose modification criteria (Section 7.9).
- T+7W to T+9W** **Weekly telephone call (RP).** Child and sleep diary reviewed. Seizure diary (if applicable) and TESS review. Medication dose maintained, no further increases permitted. Dose reductions are permitted if required (Section 7.9.2).
- T+10W** **Weekly telephone call (RP).** Child and sleep diary reviewed. Seizure diary (if applicable) and TESS review. Reminder to obtain salivary melatonin assay during this week. **Second and final collection of saliva takes place at the beginning of the eleventh week (ideally on the evening following the T+10 telephone call) of treatment and MUST occur one night after NO melatonin that or the previous night.**
- T+11W:** **Home visit 6 (RP).** Child and sleep diary reviewed. Seizure diary (if applicable) and TESS review. Application of actigraph for final week of study treatment. RP will collect unused medication from weeks T+5W to T+11W (sufficient capsules to be retained by family for final week of therapy).
- T+12W:** **Clinic visit (Clinician review).** Study completion. Child and sleep diary reviewed. Seizure diary (if applicable) and TESS review. Actigraph data downloaded and visually compared with the sleep diary. Reasons for major discrepancies with the sleep diary recorded. Actigraph unit collected; parents to complete the same questionnaires as completed at T0W

The RP will be available by telephone between the formal reviews to give advice and support regarding the practicalities of the study but will not give advice on sleep management.

Table 2. Schedule of Study Procedures

Time (T) (Weeks)		-4	-2	0*	1	2	3	4	5 & 6	7 to 9	10	11	12	
Procedures		Screening (Clinic visit)	Home visit	Clinic visit	Home visit	Home visit	Home visit	Home visit	Tel. call	Tel. call	Tel. call	Home visit	Study completion (Clinic visit)	Premature Discontinuation
Signed Informed Consent **		X ¹	X ²	X ³										
Adaptive Behaviour Assessment System		X												
Assessment of Eligibility Criteria		X	X	X										
Review of Medical History		X		X										
Registration for 4-week Sleep Hygiene		X												
Review of Concomitant Medications				X	X	X	X	X	X	X	X	X	X	X
Discussion and issue of sleep hygiene booklet		X												
Social Communication Questionnaire			X											
Sleep hygiene booklet evaluation form				X										
Randomisation				X										
Children's Sleep Habits Questionnaire		X		X										
Composite Sleep Disturbance Index (CSDI)		X		X									X	
Family Impact Module of PedsQL™				X									X	
Epworth Sleepiness Scale				X									X	
Aberrant Behaviour Checklist (ABC)				X									X	
Sleep and seizure diary (if applicable)		X	X	X	X	X	X	X	X	X	X	X		
Actigraph is worn (actigraphy)		X	X	X								X		
Study Intervention				X	X	X	X	X	X	X	X	X		
Stepwise increase in treatment dose					(X)	(X)	(X)	(X)	(X)					
Physical Exam	Complete	X		X									X	(X)
	Symptom-Directed				(X)	(X)	(X)	(X)	(X)	(X)	(X)	(X)		
	Vital Signs, weight, height	X		X	(X)	(X)	(X)	(X)	(X)	(X)	(X)	(X)	X	(X)
	Occipital head circumference	X												
Assessment of Adverse Events					X	X	X	X	X	X	X	X	X	X
Special Assay or Procedure	Salivary Melatonin			X							X			
	DNA (salivary sample)		X											

*At baseline, all procedures should be done before study intervention. **Consent to: ¹Sleep hygiene; ²DNA collection; ³Randomisation

(X) – As indicated/appropriate.

8.3 Procedures for Assessing Efficacy

Duration of night-time sleep and sleep latency will be recorded by subjective (sleep diary) and objective means (actigraphy).

8.3.1 Sleep Diary

Each A4 page of the sleep diary covers a period of one week, with one column per day. Parents document their child's bed time, time they fall asleep and final time that they wake up in the morning on the form. Parents also record the time and duration of actigraph removal, daytime naps and awakenings during the night. The diary therefore allows parental perception* of their child's sleep periods to be documented and can be crosschecked with the actigraph data.

Sleep diaries will be completed continuously between T-4W and review at T0W, continuing until study completion (T+12W) for those patients who proceed with randomisation at T0W. They will be collected by the RP during home visits or clinic attendance. The RP will retain a photo-copy of these records but will forward originals to the MCRN CTU.

*Sleep diary records parental perception of a child's sleep. Parents are not required to differentiate between periods where the child is actually asleep and periods where the child is awake but quiet e.g. not disturbing the rest of the household. Therefore parents do not have to stay awake to complete the sleep diary.

8.3.2 Actigraphy

Actigraphy is the use of accelerometers to measure human movement. This has been used world wide in a variety of research and clinical situations. The actigraph is worn on the wrist and the movement of the wrist is monitored continuously whilst it is being worn. The actigraph is very light weight and can be used on individuals of all ages for long periods of time. Wrist movement data is processed within the unit and by subsequent software programs to give an indication of general activity levels of a participant.

The use of actigraphy in sleep monitoring is now well established^(29;36). This is based on the use of algorithms to predict if the participant is asleep or awake based on levels or lack of movement. During consolidated sleep periods this can give information on for instance; total sleep and wake times, sleep onset latency, sleep efficiency and sleep quality. As the actigraph measures movement, further indicators are also available that are not available in overnight polysomnography studies nor from sleep diaries, these include: the amount of movement in sleep, the fragmentation index, circadian rhythm data, daytime nap analysis and activity during the daytime.

The actigraph should be worn continuously day and night for the first 4 weeks and the final week of the 16 week study period. The actigraph may be worn during bathing or showering. It can be worn on either wrist but the same wrist should be used throughout the study.

The RP will supply actigraphs with preloaded identification information in them for use with the individual child. The actigraph should be given to the participant at T-4W (the start of the sleep hygiene intervention) and will be retained until T0. Actigraphs will be downloaded and / or re-initialised at the T-2W and T0W visits. The

RP will download the actigraph data to a PC, via an Actigraph Reader, during home / clinic visits. On return to the office, or at the time, the RP will visually compare the output with the sleep diaries and will discuss any discrepancies with the parents on the telephone or at the visit. Reasons for major discrepancies with the sleep diary will be recorded. At T0W the actigraph will be removed, retaining it at site until T+11W when the actigraph is worn for the final week of trial treatment. Actigraphy data will be analysed when all patients have completed follow-up. Using the actigraph Sleep Analysis software the following information will be recorded for each night of the study period:

- total sleep time
- total wake time
- sleep onset latency
- number of awakenings

The actigraph monitor measures and stores data regarding body movements. Movements are scored in 1 minute epochs; all epochs that are scored above a pre-set threshold (sensitivity level) are scored as 'wake' and those that are below this threshold are scored as 'sleep'. The threshold is not set on an individual basis.

The start of sleep is determined from the actigraph as the first 10 minute interval, after bedtime (recorded in the diary) where there is no more than 1 epoch that is above the threshold (automatically calculated by the software) for determining wake, the software then considers the first minute of this 10 minute period as the time of sleep onset.

Any sleep interruptions will be determined by the actigraph by searching for 10 minute intervals in which activity in more than 1 epoch is above the threshold set automatically for determining 'wake'

Final wake-up time is recorded by parents in the sleep diary to the nearest minute

Sleep off-set is determined to be the last 10 minute period prior to 'final wake-up time' in which there was no more than 1 epoch that was above the threshold for determining wake.

The last minute of this 10 minute period will provide the sleep off-set time.

Total night-time sleep is calculated as the sum of all epochs scored as sleep from sleep onset to sleep offset.

As the actigraphy watch defines periods of sleep as periods with little/no activity it is acknowledged that periods of restless sleep may be interpreted by the unit as periods of wake. This may be of particular issue for children with motor problems. Interpretation of the actigraphy data will be informed by the sleep diaries.

8.4 Procedures for Assessing Safety

8.4.1 Expected Adverse Events (Treatment Emergent Signs and Symptoms [TESS])

Assessment of adverse effects will be undertaken weekly between weeks T0W to T12W. These reviews will be performed by the investigator at clinic attendance or the RP during home visits or via telephone assessment. Adverse effects will be assessed using Treatment Emergent Signs and Symptoms (TESS). The TESS evaluation will include the following specific signs and symptoms:

- somnolence (drowsiness)
- increased excitability
- mood swings
- seizures (new presentation or exacerbation)*

- rash
- hypothermia
- cough
- other adverse effects not listed will also be documented; the Investigator's Brochure should be referred to when assessing causality and expectedness.

*A seizure diary will be given to the parents of those children who have an established diagnosis of epilepsy, whether or not they are receiving any antiepileptic medication (see Section 8.4.2).

Signs and symptoms will be graded and reported as; no symptoms (score 0); mild symptoms (score 1); moderate symptoms (score 2) and severe symptoms (score 3). Seriousness and causality will also be assessed by the reporting researcher (see section 10).

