4.2 Secondary Outcomes

1. Total night time sleep calculated using actigraphy data
2. Sleep efficiency calculated from the actigraphy by (number of minutes spent sleeping in bed/total number of minutes spent in bed) x 100
3. Sleep onset latency (the time taken to fall asleep) calculated using actigraphy
4. Sleep onset latency (the time taken to fall asleep) calculated using sleep diaries
5. Composite sleep disturbance index scores
6. Daily global measure of parental perception of child's sleep quality
7. Behavioural problems assessed using Aberrant Behaviour Checklist (ABC)
8. Quality of Life of the care-giver assessed using the Family Impact Module of the PedsQL™
9. Level of daytime sleepiness of caregiver assessed using the Epworth Sleepiness Scale
10. Number and severity of seizures evaluated using seizure diaries throughout trial follow-up
11. Adverse effects of melatonin treatment assessed weekly between weeks T0W to T12W using 'TESS' (Treatment Emergent Signs and Symptoms) (Section 8.4.1)
12. Salivary melatonin concentrations
13. Associations between genetic variants and abnormal melatonin production

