10.2 Notes on Adverse Event Inclusions and Exclusions

10.2.1 Include

- An exacerbation of a pre-existing illness
- An increase in frequency or intensity of a pre-existing episodic event/condition

- A condition (even though it may have been present prior to the start of the trial) detected after trial drug administration
- Continuous persistent disease or symptoms present at baseline that worsens following the administration of the study/trial treatment
- Treatment Emergent Signs and Symptoms (TESS) evaluation, to include the following specific signs and symptoms:
 - somnolence
 - increased excitability
 - mood swings
 - seizures (new presentation or exacerbation)*
 - rash
 - hypothermia
 - cough
 - other adverse effects not listed will also be documented; the Investigator's Brochure should be referred to when assessing causality and expectedness.

*A seizure diary will be given to the parents of those children who have an established diagnosis of epilepsy, whether or not they are receiving any antiepileptic medication (see Section 8.4.2).

Signs and symptoms will be graded and reported as; no symptoms (score 0); mild symptoms (score 1); moderate symptoms (score 2) and severe symptoms (score 3). Seriousness and causality will also be assessed by the reporting researcher (see section 10.3).

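### TESS symptoms get no 0–3 grade before the first dose, although the reporting rules turn on whether a symptom was present at baseline and worsened

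*Protocol*

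**What the plan says.** Section 4.2 lists as a secondary outcome "Adverse effects of melatonin treatment assessed weekly between weeks T0W to T12W using 'TESS", and section 9.3.2 carries the same entry. Section 8.4.1 gives the procedure: "Assessment of adverse effects will be undertaken weekly between weeks T0W to T12W". It names seven signs and symptoms plus an open category, each scored from 0 to 3 ("Signs and symptoms will be graded and reported as; no symptoms (score 0); mild symptoms (score 1" and so on up to severe).

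Section 8.2 turns this into visits. At T0W it says "The following baseline questionnaires and assessments will be carried out after consent and prior to randomisation", followed by five instruments: CSDI, CSHQ, the PedsQL Family Impact Module, the Epworth scale and the ABC. TESS is not among them. It first appears at the T+1W home visit: "Child and sleep diary reviewed; medication increased or maintained*, based upon sleep diaries; TESS review; seizure diary review". In Table 2 the row "Assessment of Adverse Events" has no mark before week 1.

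Section 10.2.1 includes as an adverse event "Continuous persistent disease or symptoms present at baseline that worsens following the administration of the study/trial treatment". Section 10.2.2 is the mirror image: conditions that were there before treatment and have not worsened are not to be recorded.

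**The concern.** The outcome is called treatment emergent, and the reporting rules are rules about change from the pre-treatment state. The instrument that grades the symptoms is first read on treatment. If a parent reports moderate drowsiness or mood swings at T+1W, the record holds no earlier TESS grade showing whether this is new, worse or unchanged. Staff must rely on recall and on other records that were not made on this scale.

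In children with impaired sleep and developmental delay, some with epilepsy or autistic spectrum disorder, several of these symptoms are plausible before any drug is given. At stake are the classification of individual events and the interpretation of the absolute rates. A grade not taken before dosing cannot be recovered afterwards by any analysis rule.

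**Working it through.** The protocol states no figure for this outcome, so the check is mainly a comparison of passages.

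**1. Is the week-0 gap in Table 2 real, or a shifted column?** Reading both rows against the same header:

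| Row | Marks | First mark | Last mark |
|---|---|---|---|
| "Assessment of Adverse Events" | 10 | week 1 | premature discontinuation |
| "Review of Concomitant Medications" | 11 | week 0 | premature discontinuation |

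The two rows agree in every column from week 1 onward and differ only at week 0. The gap is therefore real and agrees with the T0W text in section 8.2. Scheduled TESS gradings before the first dose: 0. The Table 2 footnote places all baseline procedures before the study intervention, so a single mark at week 0 would have secured a pre-dose grade.

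**2. Which items need a pre-dose grade?** Of the seven named items in section 8.4.1, two already express change: excitability is qualified as increased, and seizures are limited to new or exacerbated ones. The other five (somnolence, mood swings, rash, hypothermia, cough) are bare symptoms.

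**3. What pre-dose information exists for them?**
- Somnolence: daytime naps in the sleep diary from T-4W (section 8.3.1), but no severity grade.
- Mood swings: the ABC at T0W measures baseline behaviour (section 8.6.2.4), on a different scale.
- Rash and cough: medical history and complete physical examination at T0W (Table 2), without a 0–3 grade.
- Hypothermia: vital signs at T0W, assuming that these include temperature.
- Seizures: diaries from T-4W to T0W (section 8.4.2), recording number, type and sleep state, for children with established epilepsy only.

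None of these is a TESS grade, but several help.

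**4. What does the gap do to the rates?** For one item, let p be the proportion with the symptom before treatment, q the proportion of symptom-free children who develop it, and f the fraction of pre-existing, unchanged cases wrongly counted as emergent. Assume that p and f are the same in both arms. The reported rate in an arm is then

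f·p + (1 − p)·q.

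- Overstatement of the absolute rate is f·p in each arm, from 0 (f = 0, section 10.2.2 applied perfectly) up to p (f = 1, never applied).
- The difference between arms is (1 − p)(q₁ − q₀) for any f, because f·p cancels. The risk difference over all randomised children is therefore not shifted by f.
- The ratio of the two rates moves towards 1 as f·p grows. While the rates stay below one half, the binomial variance also rises, so precision falls.

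Error can also run the other way: a pre-existing symptom that did worsen may be set aside as old. The protocol gives no value for p, q or f, so these effects have a direction but no estimable size.

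**The case against.** The strongest reply has four parts.

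**The window may be an interval.** Weekly assessment between T0W and T12W can mean the period covered, with reviews from T+1W to T+12W, which is what the schedule provides. Section 7.8.1 uses similar wording for the weekly review of concomitant medication. This stands, and it makes the contradiction with section 8.2 a soft one. Section 7.8.1, however, separately states a collection at T0W. For TESS there is none, so the missing baseline remains on either reading.

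**Staff are told to separate old from new and have data to do it.** Also true in part. Section 10.2.2 gives the instruction, and T0W supplies the ABC, history, examination and vital signs. It would be wrong to say that there is no baseline information. What is missing is a grade on the scale used afterwards.

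**The arms are treated alike.** Correct. The schedule is blinded and common to both arms, so a reader should not infer between-arm bias.

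**The analysis rule belongs in the SAP.** The definition of emergent may well be there. Collecting the grade cannot be.

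Two stronger readings are tempting. A reader might infer that the dose-step review is undermined at T+1W. Section 7.9.1 has the research practitioner review TESS, but none of its five criteria for an increase uses a TESS grade or a change in one, and the seizure criterion can draw on pre-dose diaries where a child has epilepsy. A reader might also infer a large loss of power. That would need invented symptom rates and staff who disregard section 10.2.2. The protocol sets no power target for TESS items.

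**Conclusion.** The point holds as a limited one. No TESS grade is scheduled before the first dose, while sections 10.2.1 and 10.2.2 need the pre-dose state. The gap matters chiefly for somnolence, mood swings, rash and cough, and existing T0W data narrow it without closing it.

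The consequences are less reliable classification of symptoms as new or worsened, absolute rates that may be overstated, and some dilution of any true difference through a ratio nearer 1 and lower precision. The documents do not permit a numerical estimate. The algebra assumes equal pre-treatment prevalence and equal misclassification in both arms, which randomisation and blinding make reasonable. This is a worthwhile, inexpensive improvement to a listed secondary safety outcome. It does not threaten the primary analysis.

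**What to change.** Add a TESS 0–3 grading, done before the first dose, to the T0W list in section 8.2, and put a mark at week 0 in the adverse-event row of Table 2. The stated window in sections 4.2, 8.4.1 and 9.3.2 then matches the schedule. Report as emergent those symptoms whose grade exceeds the child's T0W grade; this rule can sit in the protocol or the SAP.

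The cost is a few minutes at a clinic visit that already takes place, plus one schedule entry and the matching form page if it is not already there.
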